8.2. Setting

8.2.1. Inclusion criteria

Patients must meet all the following selection criteria

1. Patients registered in the MDV database 2008 though 2021.
2. Patients newly with non-valvular atrial fibrillation
3. Patients who newly receive warfarin or apixaban after diagnosis of NVAF
4. Age 20 years or older on the index date
5. Patients who have a history of stroke or TIA are inclusion criteria only for secondary prevention cohort, otherwise patients will be concluded in the primary prevention cohort.

8.2.2 Exclusion criteria

Patients who meet the following exclusion criteria will be excluded from this study

- 1 Patients with a diagnosis of valvular AF (standard disease code: 8846941), postoperative AF (8847772), AF associated with mechanical valve malfunction (T82.0), mechanical complication of heart valve prosthesis (T82.0), or rheumatic AF (I05-I09) during the baseline period.
- 2 Patients with a diagnosis of VTE during the baseline period
- 3 Patients who are prescribed any anticoagulants before index date.
- 4 Patients who are prescribed anticoagulants other than warfarin and apixaban on the index date
- 5 Patients who are continuously hospitalized due to the first incidence of stroke or other serious diseases.

8.3. Variables

- Clinical and demographic characteristics of patients eligible for this study.
- Incidence of recurrent stroke (types of stroke)
- Incidence of bleeding (any bleeding, major bleeding, intracranial stroke, gastrointestinal stroke or intraocular bleeding)
- Medicines (types of anticoagulant, anti-platelet drugs and others)
- Comorbid diseases

Table1: Variables

Variable	Role	Operational definition
Previous stroke or TIA		
Prvious incidence of stroke	Patient characteristic:	
Previous incidence of TIA	Patient characteristic:	Defined elsewhere using ICD-10 codes

Types of previous stroke	Patient characteristic:	cardioembolic stroke or cerebral infarction
Hospitalization status	Patient characteristic:	Inpatients or outpatients
Hospitalization days	Patient characteristic:	0 or days in hospital
NVAF diagnosis and treatment		
Year	Patient characteristic	Year first diagnosed with NVAF
Anticoagulant	Patient characteristic	Warfarin or apixaban
Patients		
age	Patient characteristics on index date	Years
Age category	Patient characteristics on index date	
age ≤ 65		
age $65 < , \leq 75$		
age $75 <$		
Gender category	Patient characteristics on index date	Male or female
Body weight	Baseline characteristic	Kg (if available)
Height	Baseline characteristic	cm (if available)
BMI	Baseline characteristic	Calculated from body weight and height using a formula of (weight [kg] / (height [m]) ²
Comorbidity profile		
Chronic obstructive pulmonary disease (COPD)	Baseline characteristic	Defined elsewhere using ICD-10 codes
Congestive heart disease	Baseline characteristic	Defined elsewhere using ICD-10 codes
Ischemic heart/coronary artery disease	Baseline characteristic	Defined elsewhere using ICD-10 codes
Diabetes	Baseline characteristic	Defined elsewhere using ICD-10 codes
Hyperlipidemia	Baseline characteristic	Defined elsewhere using ICD-10 codes
Hypertension	Baseline characteristic	Defined elsewhere using ICD-10 codes
Liver disease	Baseline characteristic	Defined elsewhere using ICD-10 codes
Renal disease	Baseline characteristic	Defined elsewhere using ICD-10 codes
Peripheral vascular disease	Baseline characteristic	Defined elsewhere using ICD-10 codes
Pregnancy	Exclusion criteria	Presence of "pregnancy"-related ICD-10 codes.
Cancer	Baseline characteristic	Defined elsewhere using ICD-10 codes

VTE	Baseline characteristic (exclusion criteria)	Defined elsewhere using ICD-10 codes
Medicines		
Anti-hypertensive drugs	Baseline characteristic	Defined elsewhere using drug codes
Anti-platelet drugs	Baseline characteristic	Defined elsewhere using drug codes
NSAIDs (chronic use*)	Baseline characteristic	Defined elsewhere using drug codes
Statins	Baseline characteristic	Defined elsewhere using drug codes
Outcomes		
Ischemic stroke (1)+(2)	Outcome	Defined elsewhere using ICD-10 codes
(1) Cardiogenic cerebral embolism	Outcome	Defined elsewhere using ICD-10 codes
(2) Cerebral infarction	Outcome	Defined elsewhere using ICD-10 codes
Hemorrhagic stroke	Outcome	Defined elsewhere using ICD-10 codes
Systemic embolism	Outcome	Defined elsewhere using ICD-10 codes
Bleeding	Outcome	
Major bleeding (Any bleeding requiring hospitalization)	Outcome	Refer to SAP
Intracranial hemorrhage	Outcome	Defined elsewhere using ICD-10 codes
Gastrointestinal tract bleeding	Outcome	Defined elsewhere using ICD-10 codes
Intraocular bleeding	Outcome	Defined elsewhere using ICD-10 codes

*NSAIDs chronic use

Patients who have been prescribed NSAIDs at least for 90 days during the baseline period. For non-oral drugs, the difference between each prescription day is counted as the number of prescription days.

8.4. Data sources

Medical Data Vision database

This study will use an anonymized Medical Data Vision Co. Ltd. (Tokyo, Japan, MDV) database from 450 acute care hospitals nationwide in Japan (as of June 2021) (23% of acute care hospitals with a combined diagnostic procedure (DPC) system). The MDV database consists of

administrative claims data on approximately 37 million individuals maintained in inpatient and outpatient settings. Each patient is associated with a specific ID to which all inpatient and outpatient data is linked.

8.5. Study size

In this study, eligible patients will be aggregated backward.

- The number of estimated patients;
- All registered patients: approximately 38 millions (2008-2021)
- Patients with ischemic stroke: 1.2 millions
- Patients with atrial fibrillation: 1.3 millions
- AF patients with a history of ischemic stroke: 226,000
- AF patients on warfarin: 251,000
- AF patients on apixaban: 237,000
- The number of patients who experienced recurrent ischemic stroke on warfarin or apixaban: unknown

8.6. Data management

The data will be provided by MDV. All the data is already structured in the database, so there is no need for new database development or manual review. The provided data can be used as-is for analysis. Therefore, there is no need for data management.

All analyses will be conducted using SAS software (Version 9.0 or higher, SAS Institute, Cary, NC, USA), and findings are presented in charts and tables created in Microsoft Excel.

8.6.1. Case report forms (CRFs)/Data collection tools (DCTs)/Electronic data record

Not applicable

8.6.2. Record retention

Not applicable

8.7. Data analysis

The detailed methodology for data analysis will be described in the Statistical Analysis Plan (SAP).

As a first step, extracted patients will be divided into two cohorts, primary prevention cohort and secondary prevention cohort based on the previous diagnosis of stroke. Clinical and demographic characteristics will be compared with two cohorts at baseline and on the index date (date of the initiation of warfarin and apixaban) and incidence rates of stroke/SE and major bleeding per 1,000 person-years will be calculated during follow-up period. In addition, interaction analysis will be conducted to investigate an interaction between OAC (warfarin/apixaban) and presence or absence of the previous episode of stroke.

- As a second step, only secondary prevention cohort will be used for further analyses as follows, Crude (before IPTW) patient characteristics are compared between warfarin and apixaban cohorts using appropriate methods (continuous variables: unpaired t-test or Mann-Whitney U-test, categorical variables: chi-square test)
- A propensity score is calculated based on multinomial logistic regressions in order to account for confounding effects and to ensure that patient characteristics are balanced between the warfarin cohort and apixaban cohort. An inverse probability of treatment weighting (IPTW) method using the calculated propensity score will be applied. To avoid sample size inflation and to ensure appropriate estimation of variances, s-IPTW (stabilized IPTW) is used here.
- Balanced (after IPTW) patient clinical and demographic characteristics are shown. Covariate balance between apixaban and warfarin cohorts after s-IPTW is assessed in terms of the standardized differences with a threshold of 0.1
- Kaplan Meier curves of balanced cohorts for each endpoint are drawn.
- Incidence rates of endpoints are calculated and shown per 1000 person-years.
- Hazard ratios with 95% confidence intervals will be calculated using a Cox proportional hazards regression model that incorporate only the index OACs as independent variables.

8.8. Quality control

This study is a retrospective analytical study using quality-controlled data in a pre-existing database, and primary data collection will not be conducted. As for the data provided, quality of the data is guaranteed by MDV Co. Ltd., which has professional teams specialized in the maintenance and improvement of data quality. All these processes are consistently managed in-house. All of operations for data management in MDV Co. Ltd. are conducted in accordance with standard operational procedures of MDV Co. Ltd. For quality assurance of analysis, the vendor

which deals with the analysis will conduct code review of all modules of program, descriptive statistics review of all variables and patients row data examination of all output results in a test phase.

Statistical analysis will be also outsourced to a specialist (a vendor specialized to the statistics). Validity of analysis programs and the obtained results will be confirmed by the vendor according to the internal standard of procedures.

8.9. Limitations of the research methods

Our study, like most retrospective analyses using claims data, has several intrinsic limitations and certain expected biases.

1. The data we will use is obtained from a claims database containing information provided by hospitals applying the flat-fee payment system, which are mostly large hospitals responsible for acute care. Therefore, a significant proportion of the patients included in the present analysis will be likely in poorer health than the average population requiring hospitalization, possibly having more comorbidities and higher risk of stroke and bleeding.
2. The claims data we will use here do not include vital signs or laboratory data such as blood pressure, international normalized ratio values, and renal function parameters, which is also why we could not calculate a HAS-BLED score. These variables will not be considered in the calculation of the propensity score, and there is no guarantee that such characteristics are fully balanced after s-IPTW. Therefore, although we will compute a propensity score based on multiple variables that may affect the risk of stroke and bleeding, the influence of unexamined confounding factors will not be fully excluded.
3. We will not provide an estimation of follow-up loss, as we will have no subsequent data on patients who visited a different hospital or clinic after being registered with one of the hospitals contributing to the MDV database. This could result in an underestimation of the incidence of stroke or major bleeding events.

8.10. Other aspects

Not applicable

9. PROTECTION OF HUMAN SUBJECTS

9.1. Patient information

This study involves data that exist in anonymized structured format and contain no patient personal information. According to the ethical guidelines for epidemiological studies in Japan, informed consent is not always required for studies by unlinkable anonymized data.

9.2. Patient consent

As this study involves anonymized structured data, which according to applicable legal requirements do not contain data subject to privacy laws, obtaining informed consent from patients by Pfizer is not required.

9.3. Patient withdrawal

Not applicable.

9.4. Institutional review board (IRB)/Independent ethics committee (IEC)

Since the MDV database is comprised of unlinkable anonymized data, IRB/IEC approval is not required according to the Pfizer's SOP/Policy and local regulations in Japan.

9.5. Ethical conduct of the study

The study will be conducted in accordance with legal and regulatory requirements, as well as with scientific purpose, value and rigor and follow generally accepted research practices described in CT24-WI-GL02-RF04 and references to any additional relevant guidance.

10. MANAGEMENT AND REPORTING OF ADVERSE EVENTS/ADVERSE REACTIONS

Although this study will examine the safety and effectiveness of specific Pfizer's product (apixaban), due to the nature of the database, individuals cannot be identified. Therefore, the management and the reporting of adverse events/adverse reactions is not required for this study.

11. PLANS FOR DISSEMINATING AND COMMUNICATING STUDY RESULTS

All final data will be shared with co-author. It is also anticipated that results from this study will generate a manuscript for submission to an local or international peer-reviewed journal. In the event of any prohibition or restriction imposed (e.g., clinical hold) by an applicable competent authority in any area of the world, or if the party responsible for collecting data from the

participants aware of any new information which might influence the evaluation of the benefits and risks of a Pfizer product, Pfizer should be informed immediately.

13. LIST OF TABLES

Table1. Variables

Table2. Categories of clinical departments

14. LIST OF FIGURES

None

ANNEX 1. LIST OF STAND ALONE DOCUMENTS

None

ANNEX 2. ENCEPP CHECKLIST FOR STUDY PROTOCOLS

Not applicable

ANNEX 3. ADDITIONAL INFORMATION

Not applicable

**1. AMENDMENTS FROM PREVIOUS VERSION(S)**

None

**2. INTRODUCTION**

[figure not shown]
*Japanese population has shown to have higher rate of incidence of stroke and stroke mortality is also higher. Patients with a history of ischemic stroke are at high risk of recurrence and require more rigorous management to prevent recurrence. The same is true for patients with non-valvular atrial fibrillation (NVAF) and treatment with anticoagulants reduces the risk of recurrent embolic stroke. However, some patients still suffer from recurrent embolic and/or ischemic stroke even if they are on anticoagulants for secondary prevention. In addition to the recurrent stroke, risk of bleeding is also higher in the patients with a history of stroke because they are often chronically treated with antiplatelet agents to prevent recurrence after cerebral infarction and with an anticoagulant after embolic stroke. Concomitant use of anticoagulant and anti-platelet agents is sometimes necessary if patients with AF experience cerebral infarction and the risk of bleedings largely enhances in these patient. Thus, patients in secondary prevention are at higher risk of both recurrent ischemic stroke and more effective and safer antithrombotic therapy should take this into account.*

[figure not shown]
**2.1. STUDY DESIGN**

*It is a non-interventional comparative observational study in which patients who meet the study criteria are selected and aggregated from the patients registered in the Medical Data Vision (MDV) database.*

In this study, analyses will be conducted in a 2-step manner. The first step is an epidemiological part and the number of patients of NVAF patients with a history of stroke (cerebral infarction, cardioembolic stroke, hemorrhagic stroke or TIA) or without a history of stroke in Japan, and clinical and demographic characteristics in each cohort will be investigated. In addition, incidence rate of stroke will be investigated in each cohort and presented as incidence rates per 1,000 person-years. Relative risk of stroke/SE and major bleeding will be estimated by using Logistic regression analysis and p for interaction between OAC (warfarin or apixaban) and a history of stroke (primary or secondary) will be calculated. In this first step, propensity score matching or IPTW will not be performed to balance the patient characteristics between cohorts.

[figure not shown]
PFIZER CONFIDENTIAL

In the second step, only the secondary prevention patients who are newly diagnosed with NVAF and initiate warfarin or apixaban for prevention of cardioembolic stroke. To balance the patient characteristics between warfarin and apixaban cohorts, an IPTW methods will be applied. Using the balanced warfarin cohort and apixaban cohort, incidence of events (stroke/SE or major bleeding) (per 1,000-year) will be calculated. Additionally, Cox proportional hazard analysis will be conducted to calculate hazard ratio + 95% confident interval.

PFIZER CONFIDENTIAL

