### 2.1.3. Treatment/cohort labels

Step-1

1. Primary prevention patients who are newly diagnosed with NVAF and initiated warfarin or apixaban (primary prevention cohort)
2. Secondary prevention patients who are newly diagnosed with NVAF and initiated warfarin or apixaban (secondary prevention cohort)

Step-2

1. Balanced Warfarin cohort of secondary prevention (warfarin cohort)
2. Balanced apixaban cohort of secondary prevention (apixaban cohort)

Patients will be assigned to each cohort based on the first prescription of oral anticoagulants after the diagnosis of NVAF (warfarin or apixaban). If the first oral anticoagulant prescribed was other than warfarin or apixaban or no oral anticoagulant was used, the patients will be excluded. Patient clinical and demographic characteristics will be balanced by using an IPTW method.

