## 7.2. STATISTICAL ANALYSES

- SAS software version 9.4 (SAS Institute Inc. NC, USA) will be used for the analysis.
- For primary effectiveness analysis and primary safety analysis (see 5.1 and 5.2), statistical tests will be performed at  $p=0.05$  (two-sided) with no adjustment for multiplicity. P values less than 0.05 will be regarded as statistically significant.
- We will conduct multiple secondary analysis as shown below and these repetitive statistical analyses may cause the "Multiple Testing Problem". Here these multiple analyses will be concluded only as an exploratory purpose and we do not intend to conclude anything from the results obtained from sub-endpoint analyses here. No multiple testing adjustment will be taken.

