### 7.2.3. Summary of Analyses

All analysis other than patient characteristics will be conducted as a two-sided p-value less than 0.05.

Patient characteristics will be compared using standardized difference as a cut-off value of 0.1.

Outcome/items to be examined	Analysis Cohort	Supports Protocol Objective Number	Subgroup	Statistical Method	Covariates/Strata	Missing Data

PFIZER CONFIDENTIAL

Patients characteristics	Cohorts in Step 1 and Step 2		None	unpaired t-test or Mann-Whitney U-test, categorical variables: chi-square test		No imputation
The incidence rates of stroke/SE and major bleeding per 1,000 person-years	Cohorts in Step 1 and Step 2		None	1000 person-years	Refer to section 5.4	No imputation
Interaction analysis	Cohorts in Step 1 and Step 2		None	Cox proportional hazards regression model	Warfarin/apixaban, primary/secondary	No imputation
Incidence rate of a composite of recurrent stroke (ischemic and hemorrhagic)/SE (primary effectiveness analysis)	Balanced cohorts	Effectiveness 1	None	1000 person-years	Refer to section 5.4	No imputation
Incidence of cardiogenic cerebral embolism (secondary effectiveness endpoint)	Balanced cohorts	Effectiveness 1	None	1000 person-years	Refer to section 5.4	No imputation
Incidence of cerebral infarction (secondary effectiveness endpoint)	Balanced cohorts	Effectiveness 1	None	1000 person-years	Refer to section 5.4	No imputation
Incidence rate of major bleeding (primary safety endpoint)	Balanced cohorts	Safety 1	None	1000 person-years	Refer to section 5.4	No imputation
Incidence rate of intracranial hemorrhage (secondary safety endpoint)	Balanced cohorts	Safety 1	None	1000 person-years	Refer to section 5.4	No imputation
Incidence rate of gastrointestinal bleeding (secondary safety endpoint)	Balanced cohorts	Safety 1	None	1000 person-years	Refer to section 5.4	No imputation
Incidence of rate of intraocular bleeding (secondary safety endpoint)	Balanced cohorts	Safety 1	None	1000 person-years	Refer to section 5.4	No imputation
Time course of proportion of a composite of the incidence of recurrent stroke (ischemic and hemorrhagic)/SE -free NVAF patients treated with warfarin or apixaban	Balanced cohorts	Effectiveness 2	None	Kaplan Meier curves	Refer to section 5.4	No imputation

PFIZER CONFIDENTIAL

Time course of proportion recurrent cardiogenic cerebral embolism-free NVAF patients treated with warfarin or apixaban	Balanced cohorts	Effectivess 2	None	Kaplan Meier curves	Refer to section 5.4	No imputation

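### The SAP gives logistic regression in 2.1 and Cox in 7.2.3 for the Step 1 drug-by-stroke-history interaction; logistic regression ignores variable follow-up, and the 7.2.3 row also lists Step 2, where the interaction cannot be fitted.

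*SAP*

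**What the plan says.** - **SAP 2.1, Step 1.** "Relative risk of stroke/SE and major bleeding will be estimated by using Logistic regression analysis and p for interaction" between anticoagulant and stroke history will be calculated. Logistic regression is the only model in that sentence, and 2.1 mentions Cox only for Step 2. The same paragraph has Step 1 stroke incidence "presented as incidence rates per 1,000 person-years" and rules out matching or weighting in this step.
- **SAP 7.2.3, interaction row.** The method is a Cox proportional hazards model, the covariates are "Warfarin/apixaban, primary/secondary", and the cohorts are those of Step 1 and Step 2. The table has no row for the Step 1 relative risk.
- **SAP 2.1, Step 2.** "In the second step, only the secondary prevention patients" enter. SAP 2.1.3 labels both Step 2 cohorts as secondary prevention.
- **Protocol 8.7.** In the first step, "interaction analysis will be conducted to investigate an interaction between OAC (warfarin/apixaban) and presence or absence of the previous episode of stroke". No model is named, and details are left to the SAP.
- **Protocol 8.1.1.7.** Follow-up ends at the earliest of discontinuation, switch, last record, an endpoint, or 2 years.
- **Status of the test.** SAP 7.2.3: "All analysis other than patient characteristics will be conducted as a two-sided p-value less than 0.05". SAP 7.2 says of the multiple secondary analyses: "Here these multiple analyses will be concluded only as an exploratory purpose". It does not name the interaction.

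**The concern.** There are three defects.

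1. One test has two models. Two programmers could each follow the SAP and report different interaction p-values. The direct conflict concerns the interaction only, because 7.2.3 has no row for the relative risk.
2. Logistic regression counts who had an event and ignores how long each patient was observed. If patients on one drug stay on treatment longer, they have more time to have an event, and the odds ratio moves away from the hazard ratio.
3. The interaction row asks for a Step 2 analysis that cannot be carried out.

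This is the only planned test of whether the apixaban-warfarin contrast differs by stroke history. The research question is whether apixaban's lower risk extends to secondary prevention. SAP 7.2.2 also leans on an interaction p of 0.71 from the randomised trial to carry a hazard ratio of 0.65 into this population. In a retrospective database study, leaving the model open allows it to be chosen after the results are seen.

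**Working it through.** **Step 2 estimability.** Take the model with intercept, drug, stroke history and their product. The four drug-by-history cells of Step 1 give a design matrix of rank 4 out of 4. In Step 2 stroke history is constant, so its column equals the intercept and the product equals the drug column. The rank is 2 out of 4, and no interaction can be estimated. This needs no assumption.

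**Inputs for the person-time check.**
- From SAP 7.2.2: hazard ratio 0.65; control rates 1.2, 1.6, 2.1 and 2.6 %/year; 15,000 secondary prevention patients.
- From Protocol 8.1.1.7: 2-year cap.
- Assumed, because neither document gives them: median persistence, exponential event and discontinuation times, equal drug arms, the primary-cohort size, and which rate belongs to which stratum. SAP 2.1 does not name the contrast of its relative risk; drug is assumed here.

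**Crude odds ratio.** With event rate l and discontinuation rate m = ln 2 / median persistence, the risk of an observed event is

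risk = l/(l+m) × (1 − exp(−2(l+m))).

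Example at 2.1 %/year with medians of 1.5 years (warfarin) and 1.7 years (apixaban):
- Warfarin: l = 0.021, m = 0.4621, risk = 0.02693.
- Apixaban: l = 0.65 × 0.021 = 0.01365, m = 0.4077, risk = 0.01845.
- Odds ratio = (0.01845/0.98155) / (0.02693/0.97307) = 0.679.
- Mean follow-up (risk / l) = 1.28 v 1.35 years.

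| Median persistence, warfarin v apixaban | OR at 1.2 / 1.6 / 2.1 / 2.6 %/year |
|---|---|
| 1.5 v 1.5 y | 0.649 / 0.648 / 0.648 / 0.647 |
| 1.5 v 1.7 y | 0.680 / 0.680 / 0.679 / 0.679 |
| 1.7 v 1.5 y | 0.619 / 0.618 / 0.618 / 0.617 |
| 1 v 2 y | 0.867 / 0.867 / 0.868 / 0.868 |

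The true hazard ratio is 0.65 throughout. The shift depends on the persistence gap and hardly at all on the event rate.

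**Interaction p with no true interaction.** The statistic is the log of the ratio of the two stratum odds ratios, divided by √Σ(1/events + 1/non-events) over the four cells. Rejection is P(|Z| > 1.96). Primary rates are 1.2 or 1.6 %/year, secondary rates 2.1 or 2.6 %/year, with 15,000, 30,000 or 60,000 primary patients.

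Example (1.6 and 2.6 %/year, 30,000 primary patients; secondary 1.5 v 1.7 y, primary 1.5 v 1.5 y): log ratio 0.0458, standard error 0.1359, z = 0.34, rejection 6.3%.

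| Persistence, warfarin v apixaban | Logistic rejection, range |
|---|---|
| Same gap in both strata | 5.0% |
| Secondary 1.5 v 1.7 y, primary 1.5 v 1.5 y | 5.7-6.7% |
| Secondary 1 v 2 y, primary 1 v 1.7 y | 5.9-7.3% |

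**Cox against logistic by simulation** (3,000 replicates per setting; 1.6 and 2.6 %/year; 30,000 primary and 15,000 secondary patients; Monte Carlo standard error about 0.4-0.5 points):

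| Setting | Cox rejection | Logistic rejection | Secondary Cox HR | Secondary OR |
|---|---|---|---|---|
| Same gap, 1 v 2 y | 4.8% | 4.5% | 0.650 | 0.867 |
| Secondary 1.5 v 1.7, primary 1.5 v 1.5 | 5.1% | 6.8% | 0.649 | 0.678 |
| Secondary 1 v 2, primary 1 v 1.7 | 5.2% | 7.5% | 0.651 | 0.869 |

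**If the contrast is secondary v primary.** The defect remains. At 2.1 v 1.2 %/year the true rate ratio is 2.1/1.2 = 1.75. With assumed medians of 1.2 years (secondary) and 1.5 years (primary), the same formula gives an odds ratio of 1.59.

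**The case against.** - **The conflict turns on grammar.** Section 2.1 ties logistic regression explicitly to the relative risk and to the interaction p only by conjunction. A programmer working from 7.2.3 would fit Cox anyway. This is fair, and it is why the reading is called natural rather than certain. Even so, 2.1 never names Cox for Step 1, no precedence rule is given, and the relative risk is logistic on any reading. Figures in both documents could not be read, so a clarification there cannot be excluded.
- **The sizes rest on assumptions.** Neither document gives persistence data, and an odds ratio of 0.87 needs a twofold difference in medians. With a milder difference between strata (secondary 1.5 v 1.7, primary 1.5 v 1.6 years), rejection is only 5.1-5.4%. This stands: the effect on the interaction p is modest. The Cox simulation also assumes non-informative discontinuation, which real data may not satisfy.
- **Cox does not remove confounding.** Step 1 is unweighted, so the drug contrast is crude under either model. This stands, and calls for an unadjusted label. A Poisson rate ratio would also respect person-time; Cox is preferred because 7.2.3 already names it.
- **The analysis is exploratory and the Step 2 entry is probably a slip.** Both are likely, and they limit the severity. A listed analysis that cannot be run should still be corrected.

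**Conclusion.** The concern holds: the text is wrong as written and should be corrected. That the interaction cannot be estimated in Step 2 is certain. The two-model conflict holds on the natural reading of SAP 2.1. The logistic relative risk is biased whenever observed time differs between the groups compared. At a true hazard ratio of 0.65 the odds ratio is 0.62-0.68 for median differences of 0.2 years in either direction, and 0.87 at 1 v 2 years. The interaction p is distorted only if the persistence gap differs by stroke history, and then modestly (5.7-7.3% against 5% in the settings examined). These sizes depend on assumed persistence, stratum rates and primary-cohort size; the textual defects do not. The effect is confined to a descriptive step, and the primary weighted Cox analyses in Step 2 are not affected.

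**What to change.** 1. In SAP 2.1, replace logistic regression with one Cox model containing drug, stroke history and their product, fitted in the Step 1 cohort separately for stroke/SE and for major bleeding.
2. In the interaction row of SAP 7.2.3, name that same model and remove Step 2 from the cohort cell.
3. Report the apixaban-warfarin hazard ratio with 95% CI in each stratum beside the interaction p, labelled as unadjusted and descriptive.

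Covariate adjustment in Step 1 is optional and not part of this change. The cost is a wording change in 2.1 and in one table row. No new data are needed.
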